#### 6.7. Efficacy Figures

Figures will be presented for IGA and PGA success rate by visit using observed data. The week 12 success rate using the same MAR multiple imputation method as used in the primary analysis will also be graphed.

Figures will also be presented for the success rate at week 12 for each subgroup using MAR multiple imputation.

#### 6.8. Efficacy Subgroup Analysis

The subgroup analyses will repeat the analysis of the three co-primary and co-secondary endpoints on all subgroups. The MAR multiple imputation method will be used to handle missing data.

For lesion count subgroup analysis, the t-tests will be done assuming unequal variances using Satterthwaite's formula for variance.

#### 6.9. Dermatology Life Quality Index

Descriptive statistics treating the (C)DLQI totals scores as a continuous measure will be presented with observed and change from baseline summaries. Counts and percentages of subjects within categorized ranges ("No effect" to "Extremely large effect") will also be presented. These summaries will be presented for the DLQI and CDLQI.

Total score is calculated assigning a numerical equivalent to each answer, and summing them across the 10 questions. Answers are scored as follows:

- Very much: 3
- A lot/Quite a lot: 2
- A little/Only a little: 1
- Not at all: 0

For question 7, answering a "Yes" scores as 3 and a "No" scores as 0, however answering "No" requires answering question 7b where "A lot," "A little," and "Not at all" as scored as normal.

Descriptive statistics treating the (C)DLQI dimensional scores as a continuous measure will also be presented with observed and change from baseline summaries. These will be presented for DLQI and CDLQI separately.

For the DLQI, dimensional scores will be calculated using the following questions:

- Symptoms and Feelings: questions 1 and 2
- Daily Activities: questions 3 and 4
- Leisure: questions 5 and 6
- Work and School: question 7
- Personal Relationships: questions 8 and 9
- Treatment: question 10

For the CDLQI, dimensions cores will be calculated using the following questions:

- Symptoms and Feelings: questions 1 and 2
- Sleep: question 9
- Leisure: questions 4, 5, and 6
- School or Holidays: question 7
- Personal Relationships: questions 3 and 8
- Treatment: question 10

RD.06.SPR.18252 - FINAL October 23, 2017

#### 7. Safety Analyses

#### 7.1. Drug Exposure

#### **Study and Treatment Duration**

Study duration will count the number of days a subject is on the study, regardless of their treatment requirements. It is calculated as study end date minus study start date plus one.

Subjects are expected to take one application per day on the study. Treatment duration for the face will be calculated as the subject's treatment end date minus treatment start date plus one; treatment duration on the trunk will be calculated as the subject's treatment end date minus treatment start date plus one.

#### **Total Applications**

Applications taken is not collected on the CRF, so to estimate the number of applications a subject took, the number of recorded missed doses will be subtracted from the number of doses the subject should have taken to arrive at the number of taken applications.

Subjects who have visits after their treatment end date record the time between in one of two different ways:

- 1. Some record a number of missed doses between treatment end and their current visit. These do not count as actual missed doses, as the subject was off treatment.
- 2. Others record "NA" or leave it missing.

Thus, the calculation of total applications on the face will be done in the following steps:

- 1. Start with the subject's treatment start date.
- 2. Chose an end date to use to calculate the starting number of doses measured on the CRF. If the subject has a non-missing recorded number of missed doses at any date after their treatment end date, use the latest date available with missed doses recorded. Otherwise, use treatment end date.
- 3. Calculate the starting number of doses as end date minus treatment start date plus 1.
- 4. From that, the total number of all missed doses on the face will be subtracted..

The calculation of total applications on the trunk will be done following the same steps, but using PGA scores and counts of missing doses on the trunk.

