	Screening Visit 1 (maximum 14 days+3 days prior to Baseline)	Baseline Visit	Week 1 Visit (±3 days)	Week 2 Visit (±3 days)	Week 4 Visit (±3 days)	Week 8 Visit (±3 days)	Week 12 Final/ET Visit ² (±5 days)
Skin Oiliness Scale (SOS) Questionnaire ¹¹		X					X
Self-assessment of facial acne improvement							X
Study drug(s) Dispensing (D) and Accountability (A)		D			D/A	D/A	A
Moisturizer/cleanser Dispensing (D)		D ¹⁰					
Dosing calendar Dispensed (D) returned and reviewed (RR)		D	RR	RR	RR	RR	RR
Exit Form ¹¹							X

- (1) Baseline visit must be performed maximum 14 days after Screening with a time window of +3 days. For women of childbearing potential, there must be at least 14 days between Screening and Baseline visits (for UPT reason). No re-screening will be allowed.
- (2) Week 12 procedures will be performed earlier in case of study discontinuation.
- (3) Confirm information at Baseline
- (4) For subject of childbearing potential only: Urine Pregnancy Tests will be performed at Screening, Baseline, Week 4, Week 8, Week 12. For pre-menstrual subjects re-confirm pre-menses status at every visit and in case of status change collect information on contraceptive method and perform a UPT. For the ones who begin menses after the Screening visit, urine pregnancy tests will be performed at the visit where there was a change in status and according to the schedule for females of childbearing potential (Baseline, Week 4, 8, 12/ET). Additional UPTs may be performed at the investigator's discretion.
- (5) Subjects 9 to 11 years of age who did not meet the criteria for moderate truncal acne at Baseline: PGA will be evaluated after baseline to allow the investigators to decide to start the treatment on the trunk if the subject develops truncal acne during the study whatever the PGA grade. Local tolerability will be assessed. The Lesion counts will not be evaluated.
- (6) Photos are not mandatory; subjects will be able to participate in the study even if they refuse to participate in photo procedures.
- (7) Collection of Adverse Events will begin after signing of the informed consent/assent form.
- (8) Medication that continues after Screening visit should be recorded on the Concomitant Medication page of the eCRF. Medical or surgical procedures occurring after Screening visit should be recorded on the Procedures page of the eCRF

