#### 7.5.1.2 Treatment Duration

Treatment duration (day) is defined as "the date of the last application on face or the trunk, whichever is later, minus the date of the first application on face or the trunk, whichever is earlier, plus one".

Treatment duration will be summarized by descriptive statistics using the SAF population.

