#### 7.5.1.3 Study Medication Usage (number of applications)

The study medication usage will be based on data collected on the CRF in terms of the number of applications applied.

Number of applications applied is calculated as the expected number of applications minus the total number of missed doses/applications during the treatment. If the number of missed doses/applications is unknown, then 50% doses will be assumed to be missed between two adjacent visits.

The expected number of applications is defined as the planned total number of applications during the exposed period.

Galderma R&D RD.06.SPR.18252 Page 21 of 25

Number of applications applied and the daily average applications applied will be summarized by treatment group for the SAF population.

In addition, study medication usage may also be summarized for the face using SAF population and for the trunk using the SAFT population separately.

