#### 1. Purpose

The purpose of this document is to give details and clarifications about the analysis as presented in the Statistical Analysis Plan dated October 5, 2015. Any changes from the planned analysis as described in that document are also detailed here, and any differences described here supersede the analysis as presented in the SAP.

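### The total-applications rule keeps its plus 1 when the end date is a visit after treatment ended, so the count can be one dose too high (85/84 = 101.2% for an on-schedule completer)

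*SAP*

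**What the plan says.** The main SAP is followed by a clarification document dated October 23, 2017, called the addendum here. Its section 1 gives it priority: "any differences described here supersede the analysis as presented in the SAP". Its section 7.1 therefore governs how exposure is computed.

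Under Total Applications, the number of applications is not collected. It is estimated as the doses that were due minus the doses recorded as missed. For subjects seen after treatment end, the addendum describes two ways of recording. The first is: "Some record a number of missed doses between treatment end and their current visit". It adds that these are not real missed doses, because treatment had stopped. The second is NA or a blank.

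The steps for the face are then:

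- Step 2: if a missed-dose number exists at any date after treatment end, "use the latest date available with missed doses recorded"; if not, use the treatment end date.
- Step 3: "Calculate the starting number of doses as end date minus treatment start date plus 1".
- Step 4: subtract all missed doses on the face.

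The trunk follows the same steps. Expected applications equal treatment duration, which is treatment end minus treatment start plus one. Compliance is total over expected applications, times 100.

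The addendum does not define treatment end date. Main SAP section 7.5.1.2 builds treatment duration on "the date of the last application on face or the trunk, whichever is later".

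**The concern.** Step 3 uses one formula for two kinds of end date. Treatment end, read as the last application, is a day on which a dose was applied, so counting both ends of the interval is correct. A visit after treatment end is not such a day. Counting both ends there puts the visit day into the numerator, while the denominator still stops at treatment end.

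Step 2 extends the end date so that off-treatment evenings recorded as missed are added in step 3 and removed again in step 4. They cancel only if the number recorded equals the number of days added. If the count covers the evenings before the visit but not the visit evening, one day is left over.

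The case is not exotic. The branch is triggered by any recorded number, including 0, so a fully compliant subject seen the day after the last dose falls into it. Total applications and compliance are reported results, and a compliance above 100% for someone who followed the regimen exactly would need explaining.

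**Working it through.** **Inputs**

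- Planned doses: 84 (SAP section 5.5). This reproduces as 12 weeks × 7 days = 84.
- Study day 1 is the day of first application, and the Week 12 target is Day 85 (SAP section 7.7).
- Application is in the evening (Protocol section 12, Dose Regimen).
- At Week 12 drug is accounted for but not dispensed (Protocol, Schedule of assessments), and the visit window is ±5 days.

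On target, the last planned dose therefore falls on the evening of Day 84 and the visit on Day 85.

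**Formulas**

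Let treatment start be Day 1, L the last dose day, V the visit day, m the real missed doses, and r the off-treatment evenings recorded as missed.

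- Addendum total when a number is recorded at V: V − 1 + 1 − m − r = V − m − r
- True total: L − m
- Excess: V − L − r
- Expected applications: L − 1 + 1 = L

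The evenings strictly between the last dose and the visit number V − L − 1. If exactly these are recorded, the excess is 1. If the visit evening is recorded too, r = V − L and the excess is 0.

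**Results with the rule as written**

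| Case | Total | Expected | Compliance |
|---|---|---|---|
| L 84, V 85, 0 recorded | 85 − 0 = 85 | 84 | 101.2% |
| L 79, V 80, 0 recorded (early edge of window) | 80 | 79 | 101.3% |
| L 89, V 90, 0 recorded (late edge of window) | 90 | 89 | 101.1% |
| L 20, V 29, 8 recorded (Days 21 to 28) | 29 − 8 = 21 | 20 | 105.0% |
| L 84, V 85, 3 real misses | 85 − 3 = 82 (true 81) | 84 | 97.6% (true 96.4%) |

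The last row matters because the extra dose is then hidden below 100%.

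**Cases in which the rule is right**

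- Count NA or blank: the end date reverts to Day 84, giving 84/84 = 100%.
- Visit evening recorded as missed: (85 − 1)/84 = 84/84, and for the early stopper (29 − 9)/20 = 20/20.
- Treatment end entered as Day 85: 85/85 = 100%.

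**Check of the proposed change** (visit date minus start date, no plus 1)

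- 85 − 1 − 0 = 84
- 29 − 1 − 8 = 20
- 85 − 1 − 3 = 81

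All three equal the true totals. If the visit evening had been counted as missed, the same change would undercount: 85 − 1 − 1 = 83, or 83/84 = 98.8%; and 29 − 1 − 9 = 19, or 19/20 = 95.0%.

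**The case against.** The strongest reply is that the error depends on a recording convention that the documents do not give. If sites count missed doses through the visit evening, the plus 1 is correct and everything cancels. The completer example also needs three things together: treatment end entered as Day 84, a visit on a later day, and a number rather than NA. The addendum presents the figure as an estimate, and SAP section 7.5 makes all safety analyses descriptive.

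Most of this stands as a limit on how often the error occurs. It does not rescue the rule. On the natural reading of treatment end as the last application, the steps give more applications than treatment days, and nothing in the addendum's sections on expected applications or compliance caps that.

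Three stronger readings are tempting and should not be drawn.

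- A reader might infer an excess well above one dose, since V − L − r grows if off-treatment evenings go unrecorded. That would be under-recording, not the plus 1, and the addendum describes no such pattern.
- A reader might infer that sites recorded numeric counts differently. The addendum distinguishes only a number from NA or blank, and attributes this to subjects. NA or blank does not produce the error.
- A reader might infer that per-protocol membership shifts, because SAP section 5.5 refers to deviations above 30% of 84 doses (25.2). The documents do not say that this criterion is taken from the total-applications count. Addendum section 3 takes exclusions from categorised deviations.

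**Conclusion.** The point holds as a small derivation error. When step 2 selects a visit after treatment end, step 3 counts one application too many unless the visit evening was recorded as missed. This rests on three assumptions: treatment end is the last application date, the visit comes before that evening's dose, and a number (including 0) is recorded at the visit.

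The size is one application per affected subject when every off-treatment evening before the visit is recorded. That is about 1.2 percentage points for a completer and more for early stoppers, whose denominator is smaller. The share of subjects affected cannot be worked out from the documents. Only descriptive exposure and compliance summaries are touched; no efficacy endpoint is affected, and nothing indicates a difference between arms.

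**What to change.** - Split step 3. Keep the plus 1 when the end date is the treatment end date. When it is a later visit, use visit date minus treatment start date.
- First check the CRF completion instructions. If they count the visit evening in the missed-dose number, keep the plus 1 for visit dates as well, and say so in the addendum.
- State that treatment end date means the last application date.
- Cap total applications at treatment duration. This is only a backstop: it would not correct the subject with three real misses (82 against a true 81), so the change to step 3 is still needed.
- Apply the same to the trunk.

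The cost is one derivation change with its wording and a check of the CRF instructions. Affected totals fall by about one application. The change concerns how exposure is computed, not how the drug is used.

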#### **Expected Applications**

A subject's expected number of applications will assume that subjects take one application per day of treatment duration. Thus, a subject's expected applications is equal to their treatment duration.

#### **Compliance**

Compliance percentage will be calculated as a subject's total applications divided by their expected applications multiplied by 100.

#### 7.2. Medication Usage

A subject's average daily medication usage (g/day) will be calculated as their total medication usage divided by their overall treatment duration. Overall treatment duration is calculated as the subject's treatment end date minus their treatment start date plus one.

As per Galderma's clinical supply process, the weight of each dispensed tube is assigned based on the average weight of a sample of kits from each batch. Hence, it is possible that some subjects are recorded as having returned more grams of drug than they were dispensed. If a subject's total medication usage is negative, it will be set to zero.

#### 7.3. Adverse Events

A treatment-emergent adverse event is defined as an adverse event that occurred, or increased in severity, on or after the date of the first does of study drug. Events with missing severity will be considered severe; events with missing relatedness data will be considered related to the study drug.

Adverse events of special interest will be summarized, and are defined as follows:

- Out-of-range laboratory results that are identified as clinically significant and related to the study drug,
- Related cutaneous AEs which lead to permanent treatment discontinuation, and
- Suspicion of allergic reaction suspected to be related to the study drug.

Severe adverse events are defined as those with severity marked as "Severe" on the CRF. Adverse events related to study drug or protocol procedure are defined as those marked as having a "reasonable possibility" of being related to study drug or protocol procedure, respectively, on the CRF.

A listing of pre-treatment adverse events will be included. Pre-treatment adverse events are those with an onset date prior to the date of the first application of study drug.

#### 7.4. Local Tolerability

Local tolerability will be summarized by visit on the face and trunk separately. Summaries will present descriptive statistics of local tolerability scores when treated as a continuous measure, as well as counts and percentages of subjects with each score treated as categorical. Categorical summaries of scores that are worsened from baseline will also be presented.

Worsened from baseline is defined as having a local tolerability assessment at the summarized time point that is greater than the local tolerability assessment at baseline.

Subgroup analysis of local tolerability scores will be presented separately for the face and trunk. These summaries will treat the scores as categorical, and will present scores that have worsened from baseline for both the final and worst scores per subject.

Local tolerability scores will also be presented treating the score as dichotomous. Subjects will be summarized into two categories based on their score: "None (0)" or "Mild/Moderate/Severe (1-3)," and presented at Baseline, Final visit, and their Worst score.

Graphical assessment of local tolerability will be done on all subjects, not just those with a local tolerability assessment worsened from baseline. Subgroup analysis of local tolerability will not be graphed.

#### 7.5. Laboratory Values

Laboratory values will be presented using the International System of Units (SI units).

For summary purposes, laboratory values that are listed as above or below particular thresholds will be numerically listed as above or below that threshold, respectively, by the minimum measured amount for that parameter. For example, if a parameter is measured to two decimal places, and has a result of "> 5" then, for summary purposes, the value of 5.01 will be used. Values with "<" or ">" will be classified as Low or High, respectively, unless such classifications aren't applicable for that parameter, in which case they will be classified as Normal.

Shifts in laboratory assessments will be presented from the baseline visit to the last post-baseline visit; subjects missing baseline or post-baseline laboratory data will not be included.

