#### 7.5.4 Laboratory parameters

A summary table of the categorical grade shift changes using the normal ranges from baseline to Week 12/ET will be presented for each treatment group by each laboratory category parameter using the SAF population.

Only subjects with both baseline and Week 12/ET assessments will be included in this analysis.

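### Laboratory results reported with `<` or `>` are called Low or High by their sign alone, so some can enter the shift table as abnormal without support from the normal range

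*SAP*

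**What the plan says.** Two documents bear on this: the SAP, and the document of details and clarifications that follows it (final October 23, 2017; called the addendum here). Section 1 of the addendum gives it precedence over the SAP wherever they differ.

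- **SAP 7.5.4 (Laboratory parameters)** bases the shift table on the normal ranges: "A summary table of the categorical grade shift changes using the normal ranges from baseline to Week 12/ET will be presented".
- **Addendum 7.5 (Laboratory Values)** first turns each result beyond a threshold into a number. For a result of `> 5` on a parameter measured to two decimals, "then, for summary purposes, the value of 5.01 will be used".
- It then classifies results carrying `<` or `>` by sign: they "will be classified as Low or High, respectively", "unless such classifications aren't applicable for that parameter, in which case they will be classified as Normal".
- It also sets the comparison for the table: "Shifts in laboratory assessments will be presented from the baseline visit to the last post-baseline visit".

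The addendum gives no reason for leaving the normal ranges for these results. Its next section, 7.6 (Vital Signs), uses normal reference ranges to classify vital sign parameters.

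**The concern.** A `<` or `>` sign says that the result passed a reporting threshold. That threshold need not be a limit of the normal range, so the sign alone does not show whether the result is abnormal. A reader of the shift table will take a Normal-to-High entry to mean that a subject moved above the normal range.

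SAP 4.2 lists change from baseline in laboratory tests as a safety endpoint, and the shift table is its categorical output. The protocol's schedule of assessments has laboratory tests only at Screening and at Week 12/ET. Each subject therefore contributes about two scheduled results per parameter, and one label taken from a sign can decide the cell in which the subject is counted.

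**Working it through.** **Inputs.** From addendum 7.5: the substitution rule, the sign rule and its exception. From SAP 7.5.4: the normal-range basis of the table. Neither document gives normal ranges or reporting limits, so every range below is an assumption for illustration.

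**Step 1: reproduce the plan's figure.** With threshold t and d decimals, the substituted value is t + 10^(−d) for `>` and t − 10^(−d) for `<`. For `> 5` with d = 2, this is 5 + 0.01 = 5.01, as the addendum states. For `< 5` it is 5 − 0.01 = 4.99.

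**Step 2: compare three ways of classifying.** The last column uses only what the threshold proves, and assumes that the quantity cannot be negative. The sign-rule column leaves the exception aside.

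| Result | Substituted | Assumed range | Sign rule | Substituted value against range | What the threshold proves |
|---|---|---|---|---|---|
| `> 5` | 5.01 | 3 to 5 | High | High | High |
| `> 5` | 5.01 | 1 to 4.5 | High | High | High |
| `> 5` | 5.01 | 4 to 6 | High | Normal | Normal or High |
| `> 5` | 5.01 | 6 to 10 | High | Low | Low, Normal or High |
| `< 5` | 4.99 | 5 to 40 | Low | Low | Low |
| `< 5` | 4.99 | 6 to 40 | Low | Low | Low |
| `< 5` | 4.99 | 4 to 40 | Low | Normal | Low or Normal |
| `< 5` | 4.99 | 0 to 40 | Low | Normal | Normal |
| `< 5` | 4.99 | up to 40, no lower limit | Low | Normal | Normal |
| `< 5` | 4.99 | 0 to 4 | Low | High | Normal or High |

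The sign rule is supported only when a `<` threshold is at or below the lower limit, or a `>` threshold is at or above the upper limit. In the other rows it is unsupported. In some of these it is wrong (`< 5` with 0 to 40); in others the class is open (`> 5` with 4 to 6). The rows were chosen to show the cases and say nothing about how often each occurs.

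**Step 3: follow the label into the shift table.**

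- One visit carries a sign with its threshold inside the range, and the other is a plain in-range number: the table shows a shift that the data do not establish.
- Both visits carry the same sign: no shift appears, both are labelled abnormal, and any real crossing of a limit between them is hidden.
- Baseline is wrongly labelled: the subject starts in the wrong row, so a real Normal-to-High change can appear as Low-to-High.

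**Step 4: apply the exception.** It works by parameter, not by result, and does not say when a class is applicable. If it means parameters with no meaningful lower or upper limit, the `< 5` rows with 0 to 40 and with no lower limit become Normal, which is right. It does not reach `> 5` with 4 to 6, or `< 5` with 4 to 40, because those parameters have the class in question. If the 0 to 4 row also counts as having no meaningful lower limit, it becomes Normal as well, although the true value could lie above 4.

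**The case against.** The strongest defence has four parts.

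- **Precedence.** The addendum overrides the SAP, so there is no unresolved conflict. SAP 7.5.4 still governs ordinary numeric results. This stands, but precedence settles which rule applies and not whether that rule classifies well.
- **Caution.** Addendum 7.3 counts missing severity as severe and missing relatedness as related, so flagging uncertain laboratory results could be a similar choice. No such reason is stated for laboratory values, and a wrong label at baseline can hide a change as well as create one.
- **The exception.** Read naturally, it removes the plainest errors. This partly stands; what remains is its lack of definition and the parameters that it does not reach.
- **Reach.** SAP 7.5 makes all safety analyses descriptive, and the rule applies alike to both arms. Under addendum 7.3, laboratory adverse events of special interest also require clinical significance and relatedness to study drug, so the sign rule does not define them. All of this stands.

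A reader might also infer two stronger things. One is that every result with its threshold inside the range is misclassified. The documents do not support this: `> 5` with an assumed range of 4 to 6 may truly exceed 6, so the High label is unproven but may be right. The other is that the substituted value could simply be compared with the range. That value is a convention for summaries, not a measurement, and in this example it would always give Normal, hiding any true High. Nor is the 5.01 example itself a misclassification, since it names no parameter or range.

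**Conclusion.** The point holds as a limited and conditional one. The addendum states a rule that can label a result abnormal without comparing it with its normal range, and so departs from the basis of SAP 7.5.4 without giving a reason. Many of the results concerned are better described as indeterminate than as misclassified.

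The size is unknown and may be nil: it depends on reporting limits and normal ranges that the documents do not give. The conclusion assumes that the Low and High classes feed the shift table, which is the only laboratory output described that needs them. The consequence is confined to that descriptive table. Efficacy, alpha, sample size and the adverse events of special interest are not affected.

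**What to change.** Replace the sign rule in addendum 7.5 with wording such as:

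> Values with < or > are classified against the normal range for that parameter: Low or High only if the threshold shows the result is outside the range, Normal only if it shows the result is inside the range, otherwise Not determinable.

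State also that not applicable means the parameter has no lower (or no upper) normal limit. The substituted values can stay for numeric summaries. A blinded count of `<` and `>` results by parameter, set against the normal ranges, would show whether the change alters any cell.

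The cost is a few words, a minor program change and a small extra category in the shift table. No new data are needed.
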